15 HARMS

15.1 DEFINITIONS OF ADVERSE EVENTS AND SERIOUS ADVERSE EVENTS

Definitions of adverse events (AEs) and serious adverse events (SAEs) are taken from the Office of Human Research Protections Guidance on Reviewing and Reporting Unanticipated Problems Involving Risks to Subjects or Others and Adverse Events.

Adverse event means any untoward or unfavorable medical occurrence in a participant, including any abnormal sign (for example, abnormal physical exam or laboratory finding), symptom, or disease, temporally associated with the subject's participation in the research, whether or not considered related to the subject's participation in the research.

A serious adverse event is any adverse event temporally associated with the subject's participation in research that meets any of the following criteria:

1. results in death;
2. is life-threatening (places the subject at immediate risk of death from the event as it occurred);
3. requires inpatient hospitalization or prolongation of existing hospitalization;

4. results in a persistent or significant disability/incapacity;
5. results in a congenital anomaly/birth defect; or
6. any other adverse event that, based upon appropriate medical judgment, may jeopardize the subject's health and may require medical or surgical intervention to prevent one of the other outcomes listed in this definition (examples of such events include allergic bronchospasm requiring intensive treatment in the emergency room or at home, blood dyscrasias or convulsions that do not result in inpatient hospitalization, or the development of drug dependency or drug abuse).

15.2 CLASSIFICATION OF ADVERSE EVENTS

All adverse events (AEs) will have their relationship to study intervention assessed by the Manager of the RUSVM Student Health Services (study nurse practitioner), in consultation with the study Medical Advisor, based on temporal relationship and clinical judgment.

The following guidelines will be used to describe severity:

- **Mild** – Events require minimal or no treatment and do not interfere with the participant's daily activities.
- **Moderate** – Events result in a low level of inconvenience or concern with the therapeutic measures. Moderate events may cause some interference with functioning.
- **Severe** – Events interrupt a participant's usual daily activity and may require systemic drug therapy or other treatment. Severe events are usually potentially life-

threatening or incapacitating. Of note, the term “severe” does not necessarily equate to “serious”.

The degree of certainty about causality will be graded using the categories below.

- **Related** – The AE is known to occur with the study intervention, there is a reasonable possibility that the study intervention caused the AE, or there is a temporal relationship between the study intervention and event. Reasonable possibility means that there is evidence to suggest a causal relationship between the study intervention and the AE.
- **Not Related** – There is not a reasonable possibility that the administration of the study intervention caused the event, there is no temporal relationship between the study intervention and event onset, or an alternate etiology has been established.

Adverse events will also be classified as **expected** or **unexpected**. An AE will be considered unexpected if the nature, severity, or frequency of the event is not consistent with the risk information previously described for the study intervention. Based on the information contained in the package insert for Rabivax-S, the following adverse events are considered expected:

- Local reactions (limited to the site of the injection): pain, erythema, oedema, pruritus and induration.
- Systemic reactions: fever, shivering, malaise, asthenia, faintness, dizziness, headache, myalgia, arthralgia, nausea and abdominal pain.

- Hypersensitivity or allergic reactions: anaphylaxis, urticaria, rash and erythema multiforme.

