4 STUDY DESIGN

The trial design is a single-site, two-arm, parallel-group, participant-blinded, randomized, placebo-controlled, two-sided comparative study, with an internal pilot study for blinded sample size re-estimation. Allocation to study arm will be by block randomization stratified by sex within cohort (semester) with a 1:1 allocation ratio.

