6.3 DOSING AND ADMINISTRATION

Dosing and administration of the vaccine (Rabivax-S) will be according to the package insert, following the schedule for pre-exposure prophylaxis via the intramuscular route; that is, 1 mL by intramuscular injection in the deltoid area of the arm on Day 0, Day 7 and Day 21. Dosage and administration of the placebo (sterile water for injection) will follow the same schedule and route of administration; that is, 1 mL by intramuscular injection in the deltoid area of the arm on Day 0, Day 7 and Day 21. In the event of interruption of the schedule of administration (of either the vaccine or the placebo), the schedule will be

resumed without repeating a previous dose (as per Table 3 Recommendations for Interrupted or Delayed Routine Immunization – Summary of WHO Position Papers, updated April 2018; http://www.who.int/immunization/policy/immunization_tables/en/).

Vaccine and placebo will be administered to participants at the RUSVM Student Health Services by study nurses or nurse practitioner, using a 25G (0.50 x 25mm) needle and 2 mL syringe.

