6.4 STUDY INTERVENTION COMPLIANCE

The number of doses received, and the date received, will be recorded by study personnel at RUSVM Student Health Services in Case Report Forms (CRF) for Visits 1-3. An entry will also be made in students' health records at RUSVM Student Health Services.

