11.2 ALLOCATION CONCEALMENT

Randomization cards will be created by the Principal Investigator or Study Coordinator (using the function *plotblockrand* in the package 'blockrand' in R), placed in opaque envelopes with a window, and sealed, with the sequential subject number (starting from 1 for each sex in each cohort) visible in the envelope window. On the first day of the semester, envelopes will be placed in the RUSVM Student Health Services Office. Envelopes will be drawn sequentially by study personnel at Student Health Services as participants come in for the first injection (day 0), and opened to determine allocation. After the injection is administered, the RUSVM Student Health Services member will complete the Case Report Form for this visit (Visit 1 CRF; Appendix D), including student name, surname, email address, allocation group, intervention actually received, date received, and the batch number and expiry date of the vaccine or diluent. An entry will be also be made in students' health records. Data from the Visit 1 CRF will be entered into a password-protected file ('Participant allocation file') in a restricted-access folder on the RUSVM network. Access to the folder will be restricted to study personnel only. When participants return for the second (day 7) and third (day 21) injections in the course, study staff at RUSVM Student Health Services will refer to the file to determine the participant's allocation. After injection, study personnel will complete CRF Visit 2 (Appendix E) or Visit 3 (Appendix F).

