11.3 BLINDING (MASKING)

Participants will be blinded to their study arm allocation. The intervention procedure will be identical for both arms (intramuscular injections at Student Health Services on days 0, 7 and 21). Participants allocated to the control group will receive an intramuscular injection

of sterile water for injection using identical syringes and needles as for the vaccine group.

The injection will be prepared in a separate room to maintain participant blinding.

Unblinding of participants will occur in circumstances in which there is a need to determine their rabies pre-exposure vaccination status; for example, in the event of a possible rabies exposure or if participants wish to undertake activities during the course of their participation in the study that would increase their risk category of rabies exposure.

Rabies post-exposure management differs between patients who have not been previously vaccinated and those who have been previously vaccinated. The ACIP-recommended treatments for patients who have not been previously vaccinated [16] are rabies immune globulin (RIG) infiltrated around the wound (if present), and four injections of rabies vaccine (one each on days 0, 3, 7 and 14). For previously-vaccinated patients, ACIP recommends that no RIG should be administered, and only two injections of rabies vaccine (one each of days 0 and 3). Thus, in the event of a suspected rabies exposure that requires post-exposure prophylaxis, participants should establish their vaccination status as soon as possible.

Participants can determine their vaccination status by contacting the Student Health Services to request access to their health records, or by contacting study personnel with access to the 'Participant allocation file' and/or Visit 1 CRF (Principal Investigator, Study Coordinator, study personnel at Student Health Services). Steps for determining vaccination status and emergency contact details of all relevant personnel will be provided

in the informed consent document and in the weekly survey sent to participants.

Participants who are unblinded will exit the study at that point.

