15.3 IDENTIFICATION OF ADVERSE EVENTS

The Study Coordinator will review the Visit 1-3 CRFs daily for participants receiving injections (dose 1, 2 or 3). The study coordinator will send a link to an online Qualtrics survey (Appendix H) by email on day 3 after the date of the injection (dose 1, 2 or 3) to all participants. Information on occurrence of expected AEs will be specifically solicited in the survey, by asking the question, “Since receiving the study injection 3 days ago, did you experience any of the following...?” and providing participants with a list of expected AEs (see **Section 15.2, Classification of adverse events** for details) from which to select. Participants will also be asked to grade the severity of any AEs (mild, moderate or severe) and the outcome (recovered/resolved without sequelae, recovered/resolved with sequelae or ongoing). Information on occurrence of other AEs (unsolicited) will be sought by asking the question, “Besides the signs listed above, have you noticed anything different since starting the study?”, and providing participants the opportunity to describe what they noticed or experienced, and grade the severity and outcome as above.

Participants will also be encouraged to report any adverse events to RUSVM Student Health Services (unsolicited adverse events). An adverse event form (Appendix I) will be completed for all adverse events reported to RUSVM Student Health Services, using the Vaccine Adverse Event Reporting System (VAERS) writable PDF form (https://vaers.hhs.gov/pdf/vaers_form.pdf). The Principal Investigator, together with the

Director of the RUSVM Student Health Services, will review and compare the reports of unsolicited adverse events (adverse event forms) against reports of solicited adverse events in the AE surveys, to avoid double capture.

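### Adverse event relatedness and duplicate reports are decided by staff with access to the allocation, and neither step is masked

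*Combined protocol and SAP*

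**What the plan says.** Section 4 describes the design as "participant-blinded, randomized, placebo-controlled", and section 11.3 (Blinding) extends blinding to no one else.

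The allocation is handled inside the clinic. Under section 11.2, Student Health Services study personnel open the envelope at the first injection. For doses 2 and 3, "study staff at RUSVM Student Health Services will refer to the file to determine the participant's allocation". Section 6.3 states: "Vaccine and placebo will be administered to participants at the RUSVM Student Health Services by study nurses or nurse practitioner". Section 11.3 names the holders of the allocation file or the Visit 1 form as the PI, the Study Coordinator and the study personnel at Student Health Services.

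Two decisions about AEs are then assigned to people in or close to that group:

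- **Relatedness (section 15.2).** It is "assessed by the Manager of the RUSVM Student Health Services (study nurse practitioner), in consultation with the study Medical Advisor", on the basis of timing and clinical judgement.
- **Duplicates (section 15.3).** The PI, jointly with the "Director of the RUSVM Student Health Services, will review and compare the reports of unsolicited adverse events", checks the clinic's AE forms against the solicited survey answers so that no event is counted twice.

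Section 15.4 uses the relatedness grade. Serious AEs go to the IRB whatever the grade, but a nonserious unexpected AE goes only if it is judged related. Section 3.2.4 defines Safety Endpoint 2 as the number of unsolicited AEs and serious AEs reported to the clinic in the four weeks after the first injection.

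**The concern.** A person who knows that an injection was sterile water has a reason to lean towards not related. A person who knows that it was vaccine has a reason to lean the other way. The same knowledge can tilt a doubtful judgement on whether a clinic report and a survey answer describe one event or two. Either tilt can produce a difference between arms where none exists, or hide one that does.

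At stake are the completeness of the safety information that the IRB receives and the credibility of any table of related events. The between-arm comparison of unsolicited events may also be affected. The efficacy conclusion is not at stake.

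**Working it through.** No figure in the plan is in dispute, and none of the sample size inputs in section 8 depends on who assesses AEs. The check is therefore a trace of each step: who decides, how that person could know the arm, and what the decision feeds.

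| Step | Who decides | Route to the arm | Masking stated | What it feeds |
|---|---|---|---|---|
| Relatedness (15.2) | Student Health Services Manager (study nurse practitioner), Medical Advisor consulted | Nurse practitioner named among those who inject (6.3); clinic study personnel hold the allocation file (11.2, 11.3) | None | IRB reporting of nonserious unexpected AEs (15.4); any related-AE summary |
| Duplicate screening (15.3) | PI with Student Health Services Director | PI has allocation access (11.3) and may create the randomization cards (11.2); Director compiles clinic data by arm (12) | None | Potentially Safety Endpoint 2 |
| Solicited AEs and their severity (15.3) | Participant | None intended | Participant is blinded | Safety Endpoint 1 |
| Weekly illness survey (12) | Participant | None intended | Participant is blinded | Primary endpoint, Secondary Endpoints 1-5 |

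**How much discretion is there in the relatedness grade?** Section 15.2 lists alternative grounds for each category. A temporal relationship alone is enough for related. An established alternative cause alone is enough for not related. An event soon after injection that also has another plausible cause can meet both definitions, so judgement settles it. The reference is also unclear for the placebo arm. Section 6.1 attaches the term study intervention to Rabivax-S, while section 6.2 calls the placebo an intervention too. Under the narrow reading, an assessor who knows that sterile water was given could call every event not related.

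**Does the grade enter a safety endpoint?** No. Section 3.2.4 counts solicited events (Endpoint 1) and unsolicited events (Endpoint 2) whatever their cause. The grade acts through section 15.4 and through any table that the sponsor chooses to make of related events.

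**Does duplicate screening enter a safety endpoint?** It may. Section 15.3 does not say which record gives way when a form and a survey answer match. If the form gives way, the Safety Endpoint 2 count falls by one. If the survey answer is always kept, Safety Endpoint 1 is unchanged.

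**Is an assessor without allocation access available?** The Medical Advisor already takes part under section 15.2 and is not among those named in section 11.3. However, section 11.2 opens the allocation folder to study personnel in general, and nothing says that the Advisor is blinded. That has to be stated.

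**The case against.** The case for leaving the plan alone has four parts.

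1. The design is openly participant-blinded, so this is not a contradiction or an oversight about who is blinded.
2. The criteria in section 15.2 limit discretion, because timing alone can make an event related.
3. Serious AEs reach the IRB regardless of the grade.
4. Duplicate screening is a comparison with a fixed list of solicited reactions, which is largely mechanical.

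The first and third stand, and they limit the point to nonserious events and to an improvement in procedure. The second stands in part, since an event that meets both definitions is still left to judgement. The fourth is reasonable, but the rule for a match is not written down.

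A reader might infer more than the documents support:

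- **That the safety endpoints are biased through relatedness.** Neither endpoint uses the grade, and the plan specifies no between-arm comparison of related events.
- **That clinic staff who know the arm assign the diagnoses behind Secondary Endpoint 6 and start the testing behind Endpoint 7.** Section 3.2.2 requires only a recorded ICD-10 code, and section 12 says that clinic study personnel collect the episodes. Neither says who enters the code or orders a test, and the laboratory work is done under a separate protocol.
- **That the injection entry in the health record should be coded to hide the arm.** Section 6.4 says "An entry will also be made in students' health records at RUSVM Student Health Services", and section 11.3 relies on it: "Participants can determine their vaccination status by contacting the Student Health Services to request access to their health records". Coding the entry would remove a stated route to vaccination status, and staff who gave the injection would still know the arm.

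**Conclusion.** The point holds in a limited form. Relatedness is graded, and duplicates are screened, by people who have or can obtain the allocation, and the plan masks neither step. IRB reporting of nonserious unexpected AEs, any related-AE summary and potentially the Safety Endpoint 2 count are open to assessor bias.

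The size cannot be estimated. The documents give no expected number of AEs, no proportion judged related and no number of duplicates, so any numerical illustration would only restate its own assumptions.

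The conclusion rests on three assumptions:

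- The nurse practitioner in section 15.2 is among the clinic study personnel described in sections 6.3, 11.2 and 11.3.
- No document outside those available, such as the Trial Monitoring Plan, already masks these steps.
- For Safety Endpoint 1 to be untouched, the survey answer is the record kept when duplicates are found.

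The Manager in section 15.2 and the Director in sections 12 and 15.3 may or may not be the same role. The point does not depend on it.

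For Secondary Endpoints 6 and 7, only a limitation should be noted. The codes arise in a clinic whose records and study personnel hold the arm, and the documents do not say who assigns them. The trial's main conclusion is not affected.

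**What to change.** Make two amendments:

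1. **Section 15.2.** The Medical Advisor grades relatedness and expectedness from AE forms from which arm, product and batch have been removed. State that the Advisor has no access to the allocation file.
2. **Section 15.3.** Duplicate matching uses a listing by study ID that does not show the arm. State which record is kept when two match.

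Both decisions should be recorded before any unmasking of the participant concerned. The report should also carry the limitation on Secondary Endpoints 6 and 7.

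The cost is amendment wording, a listing without arm and one masking step per AE form. The masking and the grading have to fit within the 48 hours allowed for IRB reporting in section 15.4, so someone must be named to do the masking. The roles are already in the plan, and sample size, alpha and power do not change.

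The fix reduces the risk but does not remove it. The PI keeps access to the allocation file, so the listing takes the arm out of view without preventing a look-up. The procedures for learning vaccination status in section 11.3 stay as they are.

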15.3 IDENTIFICATION OF ADVERSE EVENTS

The Study Coordinator will review the Visit 1-3 CRFs daily for participants receiving injections (dose 1, 2 or 3). The study coordinator will send a link to an online Qualtrics survey (Appendix H) by email on day 3 after the date of the injection (dose 1, 2 or 3) to all participants. Information on occurrence of expected AEs will be specifically solicited in the survey, by asking the question, “Since receiving the study injection 3 days ago, did you experience any of the following...?” and providing participants with a list of expected AEs (see **Section 15.2, Classification of adverse events** for details) from which to select. Participants will also be asked to grade the severity of any AEs (mild, moderate or severe) and the outcome (recovered/resolved without sequelae, recovered/resolved with sequelae or ongoing). Information on occurrence of other AEs (unsolicited) will be sought by asking the question, “Besides the signs listed above, have you noticed anything different since starting the study?”, and providing participants the opportunity to describe what they noticed or experienced, and grade the severity and outcome as above.

Participants will also be encouraged to report any adverse events to RUSVM Student Health Services (unsolicited adverse events). An adverse event form (Appendix I) will be completed for all adverse events reported to RUSVM Student Health Services, using the Vaccine Adverse Event Reporting System (VAERS) writable PDF form (https://vaers.hhs.gov/pdf/vaers_form.pdf). The Principal Investigator, together with the

Director of the RUSVM Student Health Services, will review and compare the reports of unsolicited adverse events (adverse event forms) against reports of solicited adverse events in the AE surveys, to avoid double capture.

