3.2.4 SAFETY

OBJECTIVES	ENDPOINTS	JUSTIFICATION FOR ENDPOINTS
Safety		

 • To compare, between the same two groups, 
 1) The rate of solicited adverse events (AEs) through 3 days after each injection (dose 1, 2 and 3) 2) The rate of unsolicited adverse events and serious adverse events (SAEs) through four weeks after first injection • As a secondary objective, sub-group analysis for potential effect measure modification of safety endpoints by sex (males or females) 	
 1. Number of solicited self-reported events over three days following each injection of the following adverse events: 
 a. Local reactions (limited to the site of the injection): pain, erythema, oedema, pruritus and induration. b. Systemic reactions: fever, shivering, malaise, asthenia, faintness, dizziness, headache, myalgia, arthralgia, nausea and abdominal pain. c. Hypersensitivity or allergic reactions: anaphylaxis, urticaria, rash and erythema multiforme. 2. Number of unsolicited adverse events and SAEs reported to RUSVM Student Health Services through four weeks after first injection 	
Solicited adverse events are those adverse events listed in the package insert of the study intervention (Rabivax-S rabies vaccine)

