5.2.3 SCREEN FAILURES

Eligible students who consent to participate in the study and who present for the first injection within the first 12 weeks of the semester will be screened by study personnel at the RUSVM Student Health Services for contraindications to the vaccine, prior to

assignment to study intervention. Contraindications are described in the vaccine package insert and are defined as follows:

1. Contraindications requiring postponement of vaccination:
 - a. Fever or an acute illness
 - b. Antimalarial medication or other short-term immunosuppressive treatments
 - c. Pregnancy
 - d. Breastfeeding
2. Absolute contraindications:
 - a. Known systemic hypersensitivity to any of the vaccine components
(including neomycin)
 - b. History of life-threatening reaction to a vaccine containing any of the same substances as Rabivax-S

Individuals who fail screening because of a contraindication requiring postponement of vaccination may be rescreened once the condition is resolved, so long as they still meet the inclusion criteria for the study (a student in the VP program or the 1st or 5th semester of the DVM program) and that the intervention regimen (3-dose course on Days 0, 7 and 21) could still be completed before the semester break (to comply with this requirement, the latest time at which an individual could be rescreened is in Week 12 of the semester).

Individuals who fail screening because of an absolute contraindication will be excluded from the study.

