6.5 DISCONTINUATION OF STUDY INTERVENTION

Prior to administration of each dose of either the vaccine or placebo, participants will be assessed by personnel at the RUSVM Student Health Services for contraindications to the vaccine (see **Section 5.2.3, Screen Failures** for listed contraindications). Individuals with a contraindication requiring postponement of vaccination may return once the condition is resolved to resume the intervention for their allocated group (vaccine or placebo), so long as this occurs before study completion (see **Section 7, Participant Timeline** for definition of study completion). In the event of interruption of the schedule of administration (of

either the intervention or the control), the schedule will be resumed without repeating a previous dose (see **Section 6.3, Dosing and Administration** for details).

Participants for whom the study intervention was halted, due to absolute contraindications or other clinically-relevant event, or for whom intervention was postponed beyond the time of study completion, will remain in the study and complete the weekly illness surveys.

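### Cheap improvement, minor weight: neither adverse event survey question asks about listed reactions other than fever on 13 between-dose days, although unlisted signs are asked about

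*Combined protocol and SAP*

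**What the plan says.** Section 15.3 sends a link to an online AE survey "by email on day 3 after the date of the injection (dose 1, 2 or 3) to all participants". As quoted there, the survey has two questions.

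- The checklist of expected reactions is introduced with "Since receiving the study injection 3 days ago, did you experience any of the following". Section 15.2 gives the list: local reactions, systemic reactions such as fever, headache and malaise, and hypersensitivity reactions such as urticaria and rash.
- An open question, meant for all other AEs, reads "Besides the signs listed above, have you noticed anything different since starting the study".

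Outside this survey, several other routes exist.

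- Clinic reports (15.3): "Participants will also be encouraged to report any adverse events to RUSVM Student Health Services".
- Pre-dose check (6.5): before each dose, "participants will be assessed by personnel at the RUSVM Student Health Services for contraindications to the vaccine". The list in 5.2.3 includes fever or acute illness, and "Known systemic hypersensitivity to any of the vaccine components".
- Weekly illness survey (sections 7 and 12): it starts on day 10–14 after the first injection and asks about respiratory, diarrheal and febrile illness in the preceding week. The case definitions in 3.2.1 count feeling feverish as fever.
- Section 15.4 mentions a weekly review without stating its content.

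Safety Endpoint 1 in 3.2.4 counts solicited reactions over the three days after each injection. Safety Endpoint 2 is "Number of unsolicited adverse events and SAEs reported to RUSVM Student Health Services through four weeks after first injection".

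**The concern.** The two questions have different time windows, and the open one removes the listed signs from the longer window. An unlisted sign on day 15 is asked about in the survey sent on day 24. A rash on day 15 is not: it falls outside the checklist's window and is excluded from the open question. The reactions named in the vaccine's package insert are therefore followed less closely between doses than signs nobody expects. Nothing in the protocol explains this, and it reads like a side effect of wording.

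At stake is the completeness of the description of later-onset local and hypersensitivity reactions. Under 15.2 a listed reaction can still count as unexpected because of its severity or frequency. If it is also related, 15.4 makes it reportable to the IRB once the Principal Investigator knows of it. In these gaps, that knowledge depends mainly on the participant speaking up.

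**Working it through.** The plan gives no figure for survey coverage, so there is none to reproduce. The check is a day count.

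**Inputs.** Doses on days 0, 7 and 21 (6.3). AE survey on day 3 after each dose (15.3), so on days 3, 10 and 24. Checklist window: dose day to dose day + 3. Open-question window: day 0 to the last AE survey. First assumption: each survey is answered on the day it is sent.

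**Full course.**
- Checklist covers 0–3, 7–10 and 21–24: 4 + 4 + 4 = 12 days.
- Open question spans 0–24: 25 days.
- Days when unlisted signs are asked about and listed ones are not: 25 − 12 = 13, namely 4–6 (3 days) and 11–20 (10 days).

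**Sensitivity.**

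| Situation | Calculation | Days |
|---|---|---|
| Surveys answered L days late, recall to the day of response | (3 − L) + (10 − L), L = 1, 2, 3 | 11, 9, 7 |
| Dosing stops after dose 2 | 11 − 8 | 3 |
| Dosing stops after dose 1 | 4 − 4 | 0 |
| Dose 3 slips to day 28 | 4–6 and 11–27: 3 + 17 | 20 |

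The last row is an illustration. Late doses are allowed: "In the event of interruption of the schedule of administration (of either the vaccine or the placebo), the schedule will be" picked up again without repeating a dose.

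**Fever.** Take the preceding week as the seven days before the survey day. A first weekly survey on day 10 covers days 3–9, and later ones cover 10–16 and 17–23. A first survey on day 14 covers 7–13, then 14–20. Days 11–20 are thus covered for any start from day 10 to day 14. Days 4–6 are covered in full when the first survey falls on day 10 (or on day 11, covering 4–10), in part for day 12 or 13, and not for day 14. Fever therefore has another active question for most of the gap. The protocol does not describe the weekly survey as asking about rash, urticaria or injection-site reactions.

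**After the last AE survey.** Days 25–28 of the four-week window (28 − 24 = 4 days) have no AE survey question for any sign, listed or unlisted. The exclusion in the open question does not cause this, so these days are not counted in the 13.

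**The case against.** The strongest reply is that the plan does what it sets out to do. The checklist matches the three-day window of Endpoint 1. Section 12 assigns Endpoint 2 to reports through Student Health Services, so a listed reaction after day 3 has a designated route. The dose visits on days 7 and 21 fall immediately after each gap, and staff see the participant before injecting. A reaction that starts in the three-day window and persists is recorded as ongoing. A participant asked the open question might mention a rash anyway, and the unseen form may hold further prompts.

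Most of this stands. Both endpoints are correctly defined and nothing in their estimation changes. What remains is narrower. Clinic reporting is voluntary, and the pre-dose check as listed screens for contraindications and does not take an AE history. The survey already reaches back over these days but steers the participant away from the listed signs.

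A reader might infer that reportable events would be lost to the IRB. The documents do not support that. It would take a reaction that is listed, non-serious, related, yet unexpected in severity or frequency, confined to the gap, and mentioned neither to the clinic nor at a visit. Serious events go to the IRB whether expected or not.

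The fix could also pull in ordinary illness. At the planned control rate of 2 episodes per 26 weeks (section 8), 13 days give 2 × 13/182 ≈ 0.14 episodes per participant, or about 61 over 430 participants if that rate held in both arms. This is a count of illness episodes over the whole trial, only some of which would surface as listed signs. Excluding what was already entered in the weekly illness survey limits the duplication, but some extra work remains.

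**Conclusion.** The point holds as a cheap improvement of minor weight. On a 0/7/21 course with surveys answered on day 3, a listed reaction other than fever that begins and ends on days 4–6 or 11–20 is asked about by neither AE survey question. The size is 13 days, with the range shown above. It is a count of days; the documents give no onset times or rates, so the number of missed events is unknown.

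Two further readings are tempting and should be resisted. One is that the safety comparison is biased: both arms get the same surveys on the same schedule, and no between-arm bias is shown. The other is that 17 days (13 + 4) are lost through day 28 because of this wording: the last 4 have no AE survey for any sign.

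The conclusion rests on the question wording quoted in 15.3. The AE survey (Appendix H), the weekly survey (Appendix G) and the dose-visit forms (Appendices E and F) are not in the documents, and a prompt there could narrow the gap.

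**What to change.** Amend 15.3 and Appendix H as follows.

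1. Keep the three-day checklist unchanged for Endpoint 1.
2. In the open question, replace the opening exclusion with *Besides anything you have already reported here or in the weekly illness survey*. Keep the middle of the question, and end it with *including any of the signs above at other times? Please give the start date.*
3. Report later-onset listed reactions by arm on a separate descriptive line, outside Endpoints 1 and 2. Check them against clinic reports and weekly illness survey entries to avoid double capture.
4. Start with a new cohort. Randomization is stratified by cohort (11.1), so both arms within a cohort get the same form.

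If surveys are completed, the 13 unasked days fall to 0. An extra AE email at day 28 is not needed for this fix.

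The cost is one reworded item, one table line and an IRB-approved amendment, with no new visit. The downsides are recall of up to about 13 days on the nominal schedule (day 11 asked about on day 24), some extra relationship assessments for non-specific symptoms such as headache or malaise, and counts available only from the changed cohort onward, so safety reports by cohort would differ in capture.
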